4.0 INTRODUCTION

4.1 Background

In recent years, metabolic syndrome has been socially concerned, posing multiple risks including for coronary artery disease in association with visceral obesity-induced insulin resistance. Dyslipidemia, characteristically observed, represents a series of abnormal findings including increased TG, decreased HDL-C, sdLDL and remnant cholesterol in the blood. When one becomes highly resistant to insulin, TG increases and LDL quality alters, i.e., sdLDL with particles with small diameters increases. SdLDL is easily engulfed by macrophages and thus may accelerate formation of atherosclerotic plaque. Among other LDL, sdLDL is a small particle with the mean diameter of ≤ 25.5 nm. An overseas report showed 3-fold higher incidence of myocardial infarction in the patient population predominantly having sdLDL.¹⁾ There is another report that sdLDL was found in $\geq 70\%$ of Japanese patients with myocardial infarction²⁾, suggesting importance of measurement of particle sizes of LDL as a part of risk assessment for coronary artery disease.

Given the above situation, especially after LDL-C was successfully lowered with a HMG-CoA reductase inhibitor, it may be important to lower sdLDL in order for further reduction of coronary artery disease risk. Recently, eicosapentaenoic acid (EPA) and docosahexaenoic acid (DHA) that are omega-3 fatty acids have been highlighted as drugs having such activity. EPA and DHA have TG-lowering and antiatherosclerosis activities but the mechanism has not been completely elucidated. Omega-3-acid ethyl esters (an EPA/DHA preparation, Lotriga[®]) released in 2013 lower TG levels in a dose-dependent manner³⁾ and are expected to have the potential to lower RLP, enlarge the LDL particle size, improve FMD, and lower IL-6 levels for example.⁴⁾

The outcomes previously obtained in clinical studies for omega-3-acid ethyl esters indicated that efficacy of the product is comparable to of an EPA-E preparation in hyperlipidemic patients for which an EPA preparation is indicated. However, change and course of LDL-C after administration of omega-3-acid ethyl esters are remain to be elucidated.⁵⁾

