3 ANALYSIS SET

- Full Analysis Set
The subjects who were randomized and given at least one dose of the study drug.
- Safety Analysis Set
The subjects who are given at least one dose of the study drug.

4 CONSIDERATIONS for ANALYSIS

- Significance level, Confidence coefficient
Significance level of 5%(2-sided) will be used for analysis.
Confidence coefficient of 95% (2-sided) will be used for all confidence intervals.
- Display digit
[Mean, Confidence coefficient, Quartiles]
Round to the one digits lower than significant digits of the data.

[Standard Deviation]

Round to the 2 digits lower than significant digits of the data.

[Minimum and Maximum Values]

Display the data at the significant digits.

[Proportion, Percentage]

Round to the one decimal place.

[P-value]

Round down to four decimal places. If p-value is less than 0.0001, display “p<0.0001”

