6.2 Demographics and Other Baseline Characteristics

6.2.1 Distribution of Demographics Items

Analysis Set; Safety Analysis Set, Full Analysis Set

Analysis Variables:

Age(Week -4)(years) [Min<= - <65, 65<=Max]

Age (Week 0) (years) [Min<= - <65, 65<=Max]

Gender [Male, Female]

Height (Week -4) (cm) [Min<= - <150, 150<= - <160,
160<= - <170, 170<= - <=Max]

Weight (Week -4) (kg)
[Min<= - <50.0, 50.0<= - <60.0,
60.0<= - <70.0, 70.0<= - <80.0,
80.0<= - <=Max]

BMI(Week -4)(kg/m²)[Min<= - <18.5, 18.5<= - <25.0
25.0<= - <=Max]

Duration of Hyperlipidemia (years) [Min<5, 5<=Max]

Frequency of Fish Intake [Almost Every Day, About Every Two Days,
About Once or Twice Per Week, Rarely]

Smoking Classification [Never Smoked, Current Smoker, Ex-Smoker]

Drink Alcohol Almost Every Day? [Yes, No]

Fasting Triglycerides(Week -4)(mg/dL)
[Min<= - <300, 300<= - <=Max]

Fasting Triglycerides (Week 0)(mg/dL)
[Min<= - <300, 300<= - <=Max]

Cholesterol Concentration in sd LDL Fraction (Week 0)

Triglycerides Concentration in sd LDL Fraction (Week 0)

Free Cholesterol Concentration in sd LDL Fraction (Week 0)

Phospholipid Concentration in sd LDL Fraction (Week 0)
Particle Size (nm) of LDL (Cholesterol Monitor) (Week 0)
Particle Size (nm) of LDL (Triglycerides Monitor) (Week 0)
Particle Size (nm) of LDL (Free Cholesterol Monitor) (Week 0)
Particle Size (nm) of LDL (Phospholipid Monitor) (Week 0)

Analysis Methods: For the above analysis items, the following analysis will be performed for each treatment group and all subjects in the analysis set.

- (1) Summary of frequency distribution for discrete variables and summary statistics for continuous variables.

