7 EFFICACY EVALUATIONS

7.1 Primary Endpoint and the Analytical Methods

Analysis Set: Full Analysis Set

Analysis Variables: Change of sd LDL-C by Lipoprotein fraction and particle size of LDL

Time Point : Week 0, Week 4, Week 8

Stratified Variable: Fasting Triglycerides (Week -4)

[Min<= - <300, 300<= - <Max]

Age (Week -4) [Min<= - <65, 65<= - <Max]

Analysis Methods:

- (1) Summary statistics of observed value and 95% confidence interval for the mean will be calculated by treatment groups and time point. In addition, Mean (+/-SD) plots will be made by treatment group and time point. Mean differences and the 95% confidence interval (two-sided) will also be provided.
- (2) The same analyses described in (1) will be performed on percent change from baseline.
- (3) Subgroup analysis of observed value and percent change from baseline will be conducted by stratified variables described above. Summary statistics, 95% confidence interval for the mean, mean differences and the 95% confidence interval (two-sided) will be provided.
- (4) The same analyses described in (3) will be performed on percent change from baseline.

- (5) ANCOVA (analysis of covariance), with Fasting Triglycerides at week -4 (Min ≤ - <300, 300 ≤ - <Max), and Age at week -4 (Min ≤ - <65, 65 ≤ - <Max) as covariate, Treatment group as independent variable, will be applied to the data of percent change at Week 0 to Week 8. (alpha=0.05 through an ANCOVA strategy)

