7.2 Secondary Endpoints and the Analytical Methods

Analysis Set: Full Analysis Set

Analysis Variables:

- (1) Change of lipid component by Lipoprotein Fraction in Major Lipid
- (2) Change of fatty acid in all lipid and sd LDL-C
- (3) Change of serum lipid, lipid concentration of apolipoprotein and lipoprotein and particle number of lipoprotein

* See appendix 1 for detail of items.

Time Point: Week 0, Week 4, Week 8

Stratified Variable: Fasting Triglycerides (Week -4)

[Min ≤ - <300, 300 ≤ - <Max]

Age (Week -4) [Min ≤ - <65, 65 ≤ - <Max]

Analysis Methods: The same analyses described in 7.1 will be performed on the Items described above.

For the Analysis variable 2), exploratory analysis will be performed about relationship between percent change from baseline of sd LDL at Week 8 and percent change from baseline of fatty acid in all lipid at Week 8.

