10.1 Adjustments for Covariates

ANCOVA will be performed on primary and secondary endpoints with Fasting triglycerides at week -4($\text{Min} \leq - < 300$, $300 \leq - \leq \text{Max}$), and Age at week -4($\text{Min} \leq - < 65$, $65 \leq \text{Max}$) as covariate. Details are described in 7.1(5) and 7.2.

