1.1 Primary Endpoint

1) Change of sd LDL-C by Lipoprotein fraction and particle size of LDL

(1) sd LDL-C by Lipoprotein Fraction

Cholesterol Concentration in sd LDL Fraction

Triglycerides Concentration in sd LDL Fraction

Free Cholesterol Concentration in sd LDL Fraction

Phospholipid Concentration in sd LDL Fraction

TG/Cholesterol ratio in sd LDL Fraction

(2) Particle Size of LDL

Particle Size of LDL (Cholesterol Monitor)

Particle Size of LDL (Triglycerides Monitor)

Particle Size of LDL (Free Cholesterol Monitor)

Particle Size of LDL (Phospholipid Monitor)

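### The Week 8 percent-change ANCOVA adjusts for the two randomisation strata but not for the variable's own Week 0 value, so it loses some precision and leaves part of any chance baseline imbalance in the estimate.

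*SAP*

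**What the plan says.** SAP 7.1(5) specifies the only covariate-adjusted comparison of the primary endpoint. Fasting TG (below 300, or 300 and above) and age (below 65, or 65 and above), both from Week -4, enter "as covariate, Treatment group as independent variable, will be applied to the data of percent change at Week 0 to Week 8". This is the one analysis in 7.1 given an explicit alpha of 0.05.

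SAP 10.1 repeats the choice: "ANCOVA will be performed on primary and secondary endpoints with Fasting triglycerides at week -4", plus age. SAP 7.2 extends it to the secondary variables: "The same analyses described in 7.1 will be performed on the Items described above". Protocol 6.1 and 8.3 show that the two covariates are the randomisation strata.

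Neither document adds the Week 0 value of the analysed variable to the model, although it is available. Week 0 is a listed time point in SAP 7.1, it is the baseline for percent change (Protocol 13.1.3.1), and SAP 6.2.1 tabulates eight of the nine primary variables in Appendix 1 at Week 0. The exception is the TG/cholesterol ratio in sdLDL.

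**The concern.** Percent change still depends on the value it is divided by. Unless Week 0 and Week 8 are very highly correlated, subjects with a high Week 0 value tend to show a larger fall and those with a low value a smaller fall or a rise. The strata remove only the part of this that they explain. That part is not zero, because Protocol 4.1 links TG to LDL quality: "When one becomes highly resistant to insulin, TG increases and LDL quality alters, i.e., sdLDL with particles with small diameters increases". The rest stays in the residual.

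There are two consequences. The interval may be wider than the collected data require. And with 25 per arm, a chance Week 0 difference between arms carries into the estimate: if the treated arm happens to start higher, its fall in sdLDL-C is overstated. The direction matters. Percent change has already divided out the Week 0 value, so what remains is an over-correction through regression to the mean. SAP 6.2.1 would display such an imbalance, but the planned model could not deal with it, and adding the covariate after seeing the imbalance would be data-driven.

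**Working it through.** **Inputs from the documents.** 25 evaluable subjects per arm (Protocol 13.3); two-sided 5% level (SAP 4, "Significance level of 5%(2-sided) will be used for analysis"); response and covariates as in SAP 7.1(5). The sample size rests on feasibility, so there is no planned power or SD to reproduce.

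**Assumptions, not in the documents.** Week 0–Week 8 correlation ρ from 0.5 to 0.95; LDL size normal with CV 2%; sdLDL-C lognormal with CV 35%; 25% of subjects with TG 300 or above; 40% aged 65 or above; correlation 0.3 between TG stratum and Week 0 value; no treatment effect.

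**Approximation on the change scale.** With equal SD s at both visits:

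- Variance of change: 2(1−ρ)s². Variance after adjusting for Week 0: (1−ρ²)s². The ratio is (1+ρ)/2, multiplied by about 1 + 1/44 for one more covariate. At ρ = 0.6: 0.80 × 1.023 = 0.818.
- SE of the Week 0 difference between arms: √(2/25) = 0.283 SD.
- Change regresses on Week 0 with slope ρ−1. A one-SE imbalance at ρ = 0.6 and CV 2% therefore shifts the estimate by (0.6−1) × 0.283 × 2 = −0.226 points.
- SE of the estimate: 0.283 × √(2 × 0.4) × 2 = 0.506 points, so the shift is 0.226/0.506 = 0.45 SE. In general it is √((1−ρ)/2) SE.

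**Simulation.** 20,000 trials per setting, with allocation balanced by stratum. Percent change was regressed on arm, TG stratum and age stratum, with and without the Week 0 value. The shift columns are for the SAP's own model.

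| ρ | Variance ratio, formula | Variance ratio, LDL size | Variance ratio, sdLDL-C | Shift, LDL size (points) | Shift, sdLDL-C (points) | Shift in SE, formula |
|---|---|---|---|---|---|---|
| 0.5 | 0.767 | 0.779 | 0.825 | −0.284 | −4.70 | 0.50 |
| 0.6 | 0.818 | 0.838 | 0.858 | −0.224 | −3.82 | 0.45 |
| 0.7 | 0.869 | 0.889 | 0.902 | −0.167 | −2.80 | 0.39 |
| 0.8 | 0.920 | 0.929 | 0.939 | −0.113 | −1.88 | 0.32 |
| 0.9 | 0.972 | 0.977 | 0.977 | −0.055 | −0.95 | 0.22 |
| 0.95 | 0.997 | 0.999 | 1.000 | −0.029 | −0.47 | 0.16 |

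- In patients, for LDL size: 1/0.779 = 1.28, or 28% more at ρ = 0.5; 1/0.977 = 1.02, or 2% more at 0.9; nothing at 0.95.
- Mean 95% CI half-width at ρ = 0.6 falls from 1.01 to 0.92 points (LDL size) and from 18.3 to 17.0 points (sdLDL-C).
- With Week 0 in the model, the shift is at most 0.002 points (LDL size) and 0.08 points (sdLDL-C).
- Rejection under the null is 4.8–5.1% without Week 0 and 4.7–5.2% with it.

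**Second simulation.** A separate run used 6,000 trials per setting, lognormal CV 30% and TG correlation 0 or 0.4. Its ratios agree: about 0.78–0.80 at ρ = 0.5 and 0.97–0.99 at 0.9. It measured imbalance on the log scale, which leaves a small remainder for the skewed variable. The largest was 1.465 points per SD at ρ = 0.5, or 1.465 × 0.269 = 0.39 points for a typical imbalance, against 15.895 × 0.269 = 4.28 points without Week 0.

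**The case against.** The case for leaving the plan alone is about importance, not about the reading or the arithmetic. The trial is exploratory with a feasibility-based sample size, the test is valid and the estimate is unbiased on average. The gain depends wholly on an unknown ρ. At ρ = 0.8 the half-widths go only from 0.72 to 0.69 points (LDL size) and from 12.6 to 12.2 (sdLDL-C); at 0.9, from 0.51 to 0.50 and from 8.8 to 8.7. Such changes would hardly alter the reading of the trial. This stands as a limit on the precision argument. It does less against the imbalance argument, because the shift fades more slowly: about 0.3 SE at ρ = 0.8 and 0.2 SE at 0.9.

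The quoted gains also cannot be carried over to all the secondary variables. Some may be much more skewed, or have values set to a limit of quantification under SAP 5. With an assumed lognormal CV of 100% the variance ratio at ρ = 0.6 is 0.94, and with 40% of values at the lower limit it is 0.97; at ρ = 0.9 both are about 1.00. That stands too: the covariate does no harm there but brings less. Beyond the main grid, at ρ = 0.98, adding Week 0 costs 1–2% of variance, which is trivial.

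Finally, the Week 0 mean differences in SAP 7.1(1) and the table in 6.2.1 would reveal an imbalance. They disclose it but do not adjust for it.

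**Conclusion.** The concern holds. The planned ANCOVA omits a covariate that is already collected and is likely to be a strong predictor of percent change. The precision loss is moderate if ρ is about 0.5–0.7 (variance ratio 0.78–0.90), small at 0.9 and nil at 0.95. Over that whole range, a one-SE chance imbalance at Week 0 moves the planned estimate by roughly 0.16 to 0.5 of its standard error, and adding Week 0 removes nearly all of that. These sizes rest on assumed values of ρ and CV and apply to LDL size and sdLDL-C only. Validity is not in question. The change is worth making because it is almost free and an exploratory trial of this size depends on good estimation, but it is not critical.

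**What to change.** In SAP 7.1(5), 7.2 and 10.1, keep treatment, TG stratum and age stratum, and add the Week 0 value of the same variable as a continuous covariate. Leave the raw summaries and mean differences in 7.1(1)–(4) as descriptive output.

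In the same edit, state that the adjusted mean difference in percent change at Week 8, with its two-sided 95% CI, is the main between-group estimate, since 7.1 does not say whether the raw or the adjusted difference leads. This is a separate choice of hierarchy. It would name one such estimate for each of the nine primary variables, and the covariate should be added whether or not this statement is adopted.

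The cost is one model term (residual degrees of freedom 46 to 45 with 50 subjects) and SAP wording. No new data are needed.

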7.5 Criteria for discontinuation or withdrawal of a study subject

The principal investigator or investigator shall record the main reason for discontinuation of protocol treatment on the case report form (CRF) according to the classification described below. Refer to Section 9.1.11 for study subjects who withdraw from the study before randomization.

1. Adverse events

When the study subject had an adverse event that requires withdrawal of the study subject from the study because continued participation in the study would impose an unacceptable risk to the study subject's health, or when the study subject is unwilling to continue study participation because of the adverse event.

2. Major protocol deviation

When it is discovered after randomization that a study subject does not meet the eligibility criteria or is not adhering to the protocol, and continued participation in the study would impose an unacceptable risk to the study subject's health.

3. Lost to follow-up

When the study subject failed to make visits and could not be contacted despite the attempts to contact the study subject.

4. Voluntary termination

When the study subject wishes to withdraw from the study. The reason for discontinuation shall be obtained to the extent possible.

5. Study termination

When the sponsor or a committee such as the Ethical Review Board or regulatory authority has decided to terminate the study. Refer to Section 6.3.1 for details.

6. Pregnancy

When a female study subject was found to be pregnant.

Note: The study subject must discontinue the study immediately after she was found to be pregnant. Refer to Section 9.1.13 for the procedures.

7. Lack of efficacy

When efficacy of the study drug is not evident and continuation of the study may pose an unacceptable risk to the study subjects in the opinion of the principal investigator or investigator.

8. Others

When the principal investigator or investigator determined to terminate the study for other reasons.

The specific reasons should be recorded on the CRF.

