7.6 Procedures for discontinuation of individual study subjects

The principal investigator or investigator shall terminate a study subject's study participation when the study subject meets the criteria described in Section 7.5. Individual study subjects may discontinue their study participation without giving a reason at any time during the study. Should a study subject's participation be discontinued, the primary reason for termination shall be recorded on

the CRF by the principal investigator or investigator. In addition, efforts shall be made to perform all tests/observations/evaluations scheduled at the time of discontinuation.

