9.3.4 Completion (Visit 4) or discontinuation

Visit 4 is the last visit, and the principal investigator or the investigator shall perform the following tests, observations, and evaluations for each study subject. If the study drug administration is discontinued, study subjects should, to the extent possible, undergo tests within 3 days from the last dose taken.

Items to be checked: Food and drink consumption before visit

- Confirm that alcohol was not consumed from 9:00 pm 2 days before the visit and food was not consumed from 9:00 pm the day before the visit
 - Confirm that excessive eating/drinking and extreme change in dietary content were not made on the day before the visit.
-
- Physical examination
 - Vital signs
 - Concomitant drugs
 - Laboratory tests
 - Treatment compliance
 - Evaluation of adverse events

At completion of the clinical study, the status of all study subjects administered the study drug shall be recorded on the CRF.

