2 TIME WINDOW

For each assessment, observation and evaluation item, evaluable data is selected according to the following table. When there are multiple data exist within a time window, the one with the closest date to the reference date is adopted, and if the differences from the reference date are the same for multiple data, the later one is adopted.

< Vital Sign, Laboratory Tests, Lipoprotein Fraction >

Time Point	Reference Date	Time Allowance
		Number of Study Days
Week 0	-1	-15~-1
Week 4	28	14~41
Week 8	56	42~70

*Treated with Omega-3 FAE: The day before study drug administration is indicated as “Day -1” and “Day 1” for the administration day.

Not Treated with Omega-3 FAE: The day of visit at Week 0 is indicated as “Day -1” and “Day 1” for the next day after the visit.

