10.2 Handling of Dropouts or Missing Data

Imputation will not be performed.

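### The only model-based test uses Week 8 alone, so subjects with a Week 4 value but no Day 42–70 value drop out of it, and no missing-data sensitivity analysis is planned

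*SAP*

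**What the plan says.** - **Model.** SAP 7.1(5) specifies an ANCOVA with treatment, TG stratum and age stratum (both at Week -4), which "will be applied to the data of percent change at Week 0 to Week 8". No visit or subject term is named, so the workable reading is percent change from Week 0 to Week 8.
- **Reach.** SAP 7.2 extends this to the secondary endpoints ("The same analyses described in 7.1 will be performed on the Items described above"), and SAP 10.1 confirms it ("ANCOVA will be performed on primary and secondary endpoints").
- **Windows.** In SAP 2, "evaluable data is selected according to the following table": Week 4 is Days 14–41 and Week 8 is Days 42–70. No end-of-treatment time point is defined.
- **Missing data.** SAP 10.2 says only "Imputation will not be performed".
- **Early stopping.** Under Protocol 7.6 the investigator ends a subject's "study participation when the study subject meets the criteria described in Section 7.5". Protocol 9.3.4 adds: "If the study drug administration is discontinued, study subjects should, to the extent possible, undergo tests within 3 days from the last dose taken".
- **Lack of efficacy.** Protocol 7.5 item 7 applies "When efficacy of the study drug is not evident and continuation of the study may pose an unacceptable risk to the study subjects", in the investigator's opinion.
- **Where Week 4 data are used.** SAP 7.1(1)–(4) gives summaries and unadjusted mean differences with 95% confidence intervals by time point. SAP 6.1.3.1 tabulates completion status and reasons by arm.

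**The concern.** An early stopper can have a baseline and a Week 4 value and still contribute nothing to the test. Such an analysis is sound only if early loss is unrelated to response, given arm and strata.

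The trial is open-label with an untreated control, so the route to withdrawal need not be the same in both arms. Withdrawal for lack of efficacy is worded for the study drug and can arise only in the omega-3 arm. Adverse events are classified as drug-related only in that arm (SAP 5), although they matter here only if they go with response. Investigators also see routine laboratory results, including TG, at each visit.

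If poorer omega-3 responders leave before Day 42, the Week 8 contrast is too large; if better responders leave, it is too small. Because Protocol 13.3 bases the sample size on feasibility, the estimate is the main output, and the estimate is what would move. The tabulated reasons would show differential loss but would not correct the Week 8 result.

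**Working it through.** **1. Figures in the plan.** The only one to check is the sample size: 25 + 25 = 50. The documents state no effect size, SD, power or dropout rate, so every input in steps 3 to 6 is an assumption.

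**2. Which early stoppers are affected.** If the final sample is taken between the last-dose day and 3 days later, SAP 2 places it as follows:

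| Last dose (study day) | Window reached |
|---|---|
| 1–10 | none (10 + 3 = 13) |
| 11–13 | none or Week 4 |
| 14–38 | Week 4 only (38 + 3 = 41) |
| 39–41 | Week 4 or Week 8 |
| 42 onward | Week 8 |

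**3. Size of the shift.** Assumptions: 25 per arm; true effect -0.5 SD; correlation 0.7 between visits; baseline coefficient of variation (CV) 25%; TG at or above 300 mg/dL in 25% of subjects and age 65 or over in 40%; 1, 2 or 3 omega-3 subjects lost after Week 4; 20,000 simulated trials per scenario; Week 8 ANCOVA as in SAP 7.1(5). The scale is plausible: 0.5 × 25% = 12.5%, and dividing by each subject's own baseline raises this by about 1 + 0.25² = 1.06, to about 13.3. The simulated full-data effect is about -13.5 points, with a standard error of about 6.3.

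Loss selected on a marker correlated 0.5 with the Week 4 change:

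| Lost | Full data | After loss | Shift | Shift / 6.3 |
|---|---|---|---|---|
| 1 | -13.47 | -13.99 | 0.52 (3.9%) | 0.08 |
| 2 | -13.44 | -14.35 | 0.91 (6.8%) | 0.14 |
| 3 | -13.54 | -14.75 | 1.21 (8.9%) | 0.19 |

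With no true effect, the false-positive rate in this scenario is 5.0–5.5%.

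**4. Range for 1 to 3 lost.**
- Marker correlation 0.3: 2.0–5.2% too large; 0.7: 5.6–13.0%.
- Visit correlation 0.5: 6.1–13.4%; 0.9: 1.7–4.6%.
- Upper bound, selection on the Week 4 endpoint itself: 8.0–18.2%, at most 0.39 standard errors.
- Best responders lost on that same endpoint: 4.7–12.6% too small.
- Same 0.5 marker, equal loss in both arms: 1.4–2.9% too small.
- Random loss: 0.1% or less.

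**5. What using Week 4 does.** In the step 3 scenario:
- A likelihood-based repeated-measures model with the planned covariates gives -13.46, -13.44 and -13.50, within 0.3% of full data. Its SDs are 6.34, 6.41 and 6.46, against 6.35, 6.43 and 6.51 for the ANCOVA.
- Adding the Week 0 value gives -13.40, -13.36 and -13.42, within 0.9%, with SDs of 5.97, 6.09 and 6.17.
- The Week 8 ANCOVA with Week 0 but without Week 4 still leaves 2.4%, 4.5% and 6.2%.

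So the Week 4 data remove the shift, and Week 0 mainly adds precision. If selection instead acts through a marker correlated 0.5 with the Week 8 change, the model corrects only in part: 7.7%, 13.5% and 19.0% fall to 4.6%, 9.3% and 13.1%.

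**6. Check by a different route.** Take standardised changes with no true effect, and lose the worst fraction d of one arm on the Week 4 endpoint itself. The shift is ρφ(z_d)/(1 − d), where ρ is the correlation between the Week 4 and Week 8 changes. For ρ = 0.7 and d = 0.10 this is 0.7 × 0.1755/0.90 = 0.14 SD. Simulating 25 per arm with 2 treated subjects lost gives 0.07 SD (ρ = 0.5) and 0.11 SD (ρ = 0.7), with rejection rates of 6.0% and 7.3%. With 5 lost, it gives 0.17 and 0.24 SD, with rates of 8.7% and 13.7%. An estimate that uses Week 4 stays at zero.

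**7. Limit on scale.** Protocol Table 9.a labels the LDL fractions 28.6 to 16.7 nm. A variable confined to that range has a CV of at most (28.6 − 16.7)/(2√(28.6 × 16.7)) = 11.9/43.7 = 27%. A CV of 25% is therefore unrealistic for LDL particle size, which makes up four of the nine primary variables in SAP Appendix 1. The point values above do not carry over to them.

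**The case against.** The case for leaving the plan alone is substantial.

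- **Week 8 is a fair target.** The objective is the effect of 8 weeks of treatment, and the protocol's own primary analysis is descriptive, by time point. Nothing in the documents is contradicted. This stands, and it is why the ANCOVA should stay.
- **The gain is small.** In the step 3 scenario the ANCOVA's root mean square error is √(0.52² + 6.35²) = 6.37, then 6.49 and 6.62 for two and three lost. The model with planned covariates has 6.34, 6.41 and 6.46, a reduction of 0.5%, 1.3% and 2.4%. This also stands.
- **The route is narrow.** No visit is scheduled between Visits 3 and 4, so a Week 4 result would have to prompt an off-schedule withdrawal with the last sample before Day 42. Lack of efficacy also requires a judged unacceptable risk. Protocol 9.1.9 gives assessment of the HPLC results to the Steering Committee, so any selection would more likely act through a correlated marker such as TG. This lowers the likelihood without removing it.
- **Week 4 data are reported.** They are, but only in unadjusted summaries, which do not correct the Week 8 test.

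A reader might infer more: that the Week 8 result is biased in favour of the drug, that the type I error is materially inflated, or that a repeated-measures model must replace the ANCOVA. The documents do not support this. They show no selective loss, rate or direction, and the rejection rates of 6.0–13.7% require loss selected on the endpoint itself, with up to 5 of 25 gone from one arm.

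**Conclusion.** The gap is real and modest. It follows from the SAP text that a subject with a Week 4 value but no Day 42–70 value is excluded from the only model-based test, and that no analysis checks what this does to the result. Whether it shifts the Week 8 contrast depends on response-related early loss in one arm, which the documents neither quantify nor show.

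Under the assumed loss of 1 to 3 of 25 omega-3 subjects on a marker correlated 0.5 with the Week 4 change, the shift is about 4–9% of the effect, below 0.2 standard errors, with false positives near 5%. These are relative illustrations for a variable with a CV near 25%. This justifies a covariate and a pre-specified sensitivity analysis, because the data needed are already collected. It does not justify replacing the planned test.

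**What to change.** 1. **SAP 7.1(5), carried by 7.2 and 10.1:** keep the Week 8 ANCOVA and add the Week 0 value as a covariate.
2. **Pre-specify a sensitivity analysis**, at least for the nine primary variables: a likelihood-based repeated-measures model on Week 4 and Week 8 percent change with treatment, visit, treatment-by-visit, Week 0 value, and the TG and age strata at Week -4, using unstructured covariance and Kenward-Roger degrees of freedom. Report the Week 8 contrast.
3. **State the target.** The model estimates the Week 8 difference as if early stoppers had stayed on their assigned regimen, assuming missing at random given Week 0 and Week 4. This should be written down because the model and the observed-value Week 8 summaries in SAP 7.1(1)–(4) will stand side by side on different bases.
4. **Report the number with no Week 8 value** by arm and reason.

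SAP 10.2 can stay as written, since the model imputes nothing. The cost is SAP wording and one more model per variable: 9 for the primary set, or 9 + 63 = 72 if extended to all of Appendix 1. No new visit, sample or protocol revision is needed. The limits are partial correction if loss depends on the Week 8 response itself, and no help for subjects with no post-baseline value in a window.
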